Same as the shift analysis, for early start subjects, the placebo-controlled baseline will be used and abnormalities that occurred in either placebo-controlled or OLE period will be included. For late start subjects, the active treatment period baseline will be used and the PCS abnormalities that occurred in the OLE period based on the active treatment period baseline will be included.

Table 9: Criteria to Determine Potentially Clinically Significant (PCS) Laboratory Abnormalities

| Clinical Laboratory Outlier Criteria | | |
|--------------------------------------|----------------------------|----------------------------|
| Parameter name | PCS Low | PCS High |
| HEMATOLOGY | | |
| White blood cells | <3.0 x 10 ⁹ /L | >16 x 10 ⁹ /L |
| Lymphocytes | <0.8 x 10 ⁹ /L | >12 x 10 ⁹ /L |
| Neutrophils | <1.5 x 10 ⁹ /L | >13.5 x 10 ⁹ /L |
| Monocytes | N/A | >2.5 x 10 ⁹ /L |
| Eosinophils | N/A | >1.6 x 10 ⁹ /L |
| Basophils | N/A | >1.6 x 10 ⁹ /L |
| Red blood cells | ≤3.5 x 10 ¹² /L | ≥6.4 x 10 ¹² /L |
| Hemoglobin - Females | ≤95 g/L | ≥175 g/L |
| Hemoglobin - Males | ≤115 g/L | ≥190 g/L |
| Hematocrit - Females | ≤0.32 L/L | ≥0.54 L/L |
| Hematocrit - Males | ≤0.37 L/L | ≥0.60 L/L |

| Clinical Laboratory Outlier Criteria | | |
|---|---------------------------|-----------------------------|
| Parameter name | PCS Low | PCS High |
| Platelet count | $\leq 75 \times 10^9/L$ | $\geq 700 \times 10^9/L$ |
| BLOOD CHEMISTRY | | |
| Alanine aminotransferase (ALT) | N/A | $> 3 \times \text{ULN}$ |
| Aspartate aminotransferase (AST) | N/A | $> 3 \times \text{ULN}$ |
| Alkaline phosphatase (ALP) | N/A | $> 3 \times \text{ULN}$ |
| Total bilirubin | N/A | $> 1.5 \times \text{ULN}$ |
| Blood urea nitrogen (BUN) | N/A | $\geq 10.7 \text{ mmol/L}$ |
| Creatinine | N/A | $\geq 176.8 \text{ umol/L}$ |
| Sodium | $\leq 126 \text{ mmol/L}$ | $\geq 156 \text{ mmol/L}$ |
| Potassium | $\leq 3 \text{ mmol/L}$ | $\geq 6 \text{ mmol/L}$ |
| Chloride | $\leq 90 \text{ mmol/L}$ | $\geq 118 \text{ mmol/L}$ |
| Glucose | $\leq 2.2 \text{ mmol/L}$ | $\geq 9.7 \text{ mmol/L}$ |
| Calcium | $\leq 2 \text{ mmol/L}$ | $\geq 3 \text{ mmol/L}$ |
| Phosphorus | $\leq 0.6 \text{ mmol/L}$ | $\geq 1.7 \text{ mmol/L}$ |
| Albumin | $\leq 25 \text{ g/L}$ | $\geq 625 \text{ g/L}$ |
| Total protein | $\leq 45 \text{ g/L}$ | $\geq 100 \text{ g/L}$ |
| URINALYSIS | | |
| Glucose | N/A | $\geq 1000 \text{ mg/dL}$ |
| Protein | N/A | $\geq 100 \text{ mg/dL}$ |

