2 DESCRIPTION OF OBJECTIVES AND ENDPOINTS

The objectives and endpoints from the protocol Section 4 are described below.

| Objective | Endpoint |
|---|--|
| Primary | |
| To evaluate the efficacy of BIIB092, compared to placebo, as measured by a change from baseline in the PSP Rating Scale (PSPRS) at Week 52. | The primary efficacy endpoint will be evaluated by comparing the change from baseline in the total PSPRS score at Week 52 in participants treated with BIIB092 relative to the change from baseline in the total PSPRS score in participants treated with placebo. |
| To assess the safety and tolerability of BIIB092, relative to placebo, by measuring the frequency of deaths, SAEs, and AEs leading to discontinuation, and Grade 3 & 4 laboratory abnormalities. | The primary safety endpoint will be evaluated by tabulating the numbers and percentages of deaths and unique participants with SAEs and AEs leading to discontinuation, and Grade 3 & 4 laboratory abnormalities. |
| Key Secondary | |
| To evaluate the efficacy of BIIB092, compared to placebo, as measured by a change from baseline in the Movement Disorder Society-sponsored revision of the Unified Parkinson's Disease Rating Scale (MDS-UPDRS) Part II at Week 52. | The impact of BIIB092 on the MDS-UPDRS Part II will be evaluated relative to the change from baseline at Week 52 in the BIIB092-treated participants and compared to that of the placebo-treated participants. |
| To evaluate the efficacy of BIIB092, compared to placebo, as measured by the Clinical Global Impression of Change (CGI-C) at Week 52. | The impact of BIIB092 on the CGI-C scale score will be evaluated at Week 52 in the BIIB092-treated participants and compared to that of the placebo-treated participants. |
| To evaluate the efficacy of BIIB092, compared to placebo, as measured by a change from baseline in the Repeatable Battery for the Assessment of Neuropsychological Disease Severity (RBANS) at Week 52. | The impact of BIIB092 on the RBANS scale will be evaluated relative to the change from baseline at Week 52 in the BIIB092-treated participants and compared to that of the placebo-treated participants. |

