6.3 Clinical Laboratory Data

The following scheduled clinical laboratory parameters are to be assessed:

| | |
|--|---|
| Hematology | |
| Red blood cell count | |
| Hemoglobin | |
| Hematocrit | |
| Total leukocyte count, including differential | |
| Platelet count | |
| Serum Chemistry | |
| Aspartate aminotransferase (AST) | Total Protein |
| Alanine aminotransferase (ALT) | Albumin |
| Total bilirubin | Sodium |
| Direct bilirubin | Potassium |
| Alkaline phosphatase | Chloride |
| Lactate dehydrogenase (LDH) | Calcium |
| Creatinine | Phosphorus |
| Blood Urea Nitrogen (BUN) | Magnesium |
| Uric acid | Creatine kinase |
| Glucose | Thyroid stimulating hormone (TSH)- screening only |
| Urinalysis | |
| Protein | |
| Glucose | |
| Blood | |
| Leukocyte esterase | |
| Specific gravity | |
| pH | |
| Microscopic examination of the sediment if blood, protein or leukocyte esterase are positive on the dipstick | |
| Serology | |
| Serum for hepatitis C antibody, hepatitis B surface antigen (screening only) | |
| Other Analyses | |

| |
|--|
| INR |
| Prothrombin Time |
| Hemoglobin A1C (HbA1C)- screening only |
| Pregnancy test (WOCBP only: screening, predose, discharge). |
| Follicle stimulating hormone (FSH) (screening only for women only) |

Summaries of clinical laboratory data will be performed for scheduled laboratory parameters only. Listings of individual laboratory measurements by subjects for all the parameters, both scheduled and unscheduled, will be provided.

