6.3.2 Qualitative analyses

For all qualitative analyses, all values will be included (not just the “analyzed record” within each visit window in the quantitative analyses).

Shift analyses

Laboratory data will be summarized using shift tables where appropriate. Each subject’s hematology, blood chemistry, coagulation and urinalysis (excluding microscopic examination) values will be flagged as “low”, “normal”, or “high” relative to the normal ranges of the central laboratory or as “unknown” if no result is available. Each subject’s urinalysis values for protein, glucose, blood, and leukocyte esterase will be flagged as “abnormal” if positive, “normal” if negative, or “unknown” if no value is available.

For each parameter, the analysis will be based on subjects with at least one post-baseline value. Shifts from baseline to high/low status will be presented for hematology, blood chemistry, coagulation and urinalysis (specific gravity and pH), and shifts from baseline to abnormal (or unknown to abnormal) will be presented for urinalysis parameters (protein, glucose, blood, and leukocyte esterase). Shift to low includes normal to low, high to low, and unknown to low; shift to high includes normal to high, low to high, and unknown to high. Subjects need to have at least one post-baseline evaluation and a baseline value either unknown or not low/high/abnormal in order to be included in the analysis.

Grade analyses

Each scheduled laboratory parameter will be summarized both by worst post-baseline grade and by worst cumulative post-baseline grade; this analysis includes the primary endpoints of Grade 3 and 4 laboratory abnormalities. Subjects need to have at least one post-baseline evaluation in order to be included in the analysis. Common Terminology Criteria for Adverse Events v4.0.3 (CTCAE) published on 14 June 2010 will be used for grade determination. Grade determination is based solely on laboratory values and does not take other clinical information into account; therefore, a lower grade may be assigned to a laboratory parameter result since clinical information does not contribute to the grading assessment. Thus, the incidence of higher grades may be underestimated.

For calcium (mmol/L), the laboratory result will be corrected by the concurrent albumin (g/L) result for CTCAE grade determination. The derivation of the corrected calcium (mmol/L) will be derived as follows:

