$$\text{Corrected calcium (mmol/L)} = \frac{1}{4} * [\text{calcium(mmol/L)} - 0.8 * (0.1 * \text{albumin(g/L)} - 4)]$$

Potentially Clinically Significant laboratory abnormalities analyses

For hematology, blood chemistry and urinalysis, the number of subjects with potentially clinically significant (PCS) laboratory abnormalities post-baseline will be summarized for the parameters provided in Table 9, which also shows the thresholds used to determine PCS results. Subjects need

to have at least one post-baseline evaluation and a baseline value not PCS (including missing) in order to be included in the analysis. A listing will be provided for subjects with any PCS result post-baseline.

Table 9 Criteria to Determine Potentially Clinically Significant (PCS) Laboratory Abnormalities

| Clinical Laboratory Outlier Criteria | | |
|---|----------------------------|----------------------------|
| Parameter name | PCS Low | PCS High |
| HEMATOLOGY | | |
| White blood cells | <3.0 x 10 ⁹ /L | >16 x 10 ⁹ /L |
| Lymphocytes | <0.8 x 10 ⁹ /L | >12 x 10 ⁹ /L |
| Neutrophils | <1.5 x 10 ⁹ /L | >13.5 x 10 ⁹ /L |
| Monocytes | N/A | >2.5 x 10 ⁹ /L |
| Eosinophils | N/A | >1.6 x 10 ⁹ /L |
| Basophils | N/A | >1.6 x 10 ⁹ /L |
| Red blood cells | ≤3.5 x 10 ¹² /L | ≥6.4 x 10 ¹² /L |
| Hemoglobin - Females | ≤95 g/L | ≥175 g/L |
| Hemoglobin - Males | ≤115 g/L | ≥190 g/L |
| Hematocrit - Females | ≤0.32 L/L | ≥0.54 L/L |
| Hematocrit - Males | ≤0.37 L/L | ≥0.60 L/L |
| Platelet count | ≤75 x 10 ⁹ /L | ≥700 x 10 ⁹ /L |
| BLOOD CHEMISTRY | | |
| Alanine aminotransferase (ALT) | N/A | >3 x ULN |
| Aspartate aminotransferase (AST) | N/A | >3 x ULN |
| Alkaline phosphatase (ALP) | N/A | >3 x ULN |
| Total bilirubin | N/A | >1.5 x ULN |
| Blood urea nitrogen (BUN) | N/A | ≥10.7 mmol/L |
| Creatinine | N/A | ≥176.8 umol/L |
| Sodium | ≤126 mmol/L | ≥156 mmol/L |
| Potassium | ≤3 mmol/L | ≥6 mmol/L |
| Chloride | ≤90 mmol/L | ≥118 mmol/L |
| Glucose | ≤2.2 mmol/L | ≥9.7 mmol/L |
| Calcium | ≤2 mmol/L | ≥3 mmol/L |
| Phosphorus | ≤0.6 mmol/L | ≥1.7 mmol/L |
| Albumin | ≤25 g/L | ≥625 g/L |
| Total protein | ≤45 g/L | ≥100 g/L |
| URINALYSIS | | |
| Glucose | N/A | ≥ 1000 mg/dL |
| Protein | N/A | ≥ 100 mg/dL |
| ULN = upper limit of normal | | |

Potential serious hepatotoxicity

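### The corrected-calcium formula in placebo-controlled SAP 6.3.2 returns one quarter of the measured calcium at albumin 40 g/L, so calcium CTCAE grades programmed from it would be invalid

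*SAP*

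**What the plan says.** The primary safety endpoint (placebo-controlled SAP, Section 2) includes a tabulation of "unique participants with SAEs and AEs leading to discontinuation, and Grade 3 & 4 laboratory abnormalities". Section 6.3.2, under Grade analyses, summarizes each scheduled laboratory parameter by worst post-baseline CTCAE grade and states that "this analysis includes the primary endpoints of Grade 3 and 4 laboratory abnormalities". Grades are assigned from the laboratory value alone, without clinical information.

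Calcium gets an extra step: "the laboratory result will be corrected by the concurrent albumin (g/L) result for CTCAE grade determination". The formula follows, and its typeset source reads "1}{4} * [\text{calcium(mmol/L)} - 0.8 * (0.1 * \text{albumin(g/L)} - 4". In plain notation:

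corrected Ca (mmol/L) = ¼ × [Ca (mmol/L) − 0.8 × (0.1 × Alb (g/L) − 4)]

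Table 9 in the same section shows the range in which the SAP expects calcium to lie, through its limits for potentially clinically significant (PCS) values: "Calcium | ≤2 mmol/L | ≥3 mmol/L". Neither the protocol nor the open-label extension SAP gives another corrected-calcium formula, and the extension SAP has no CTCAE grade analysis.

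**The concern.** An albumin correction should leave calcium unchanged at the reference albumin. Here the reference is 40 g/L, where 0.1 × 40 − 4 = 0, yet the whole bracket is still divided by 4. Calcium enters in mmol/L, the albumin term is on a scale four times larger, and one conversion factor is applied to both. This is a unit-scale error.

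The stake is a component of a primary safety endpoint. With no clinical input to grading, nothing in the plan would override a wrong derived value. The consequences, if the formula is followed, would be false low grades on a large scale, high calcium that cannot register, and any real difference between arms in calcium grades obscured.

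**Working it through.** **Inputs.** The printed formula and its units come from placebo-controlled SAP 6.3.2. The limits of 2 and 3 mmol/L for calcium and the low limit of 25 g/L for albumin come from Table 9 of that section. The normal ranges used in step 5 (calcium 2.1–2.6 mmol/L, albumin 35–50 g/L) are assumptions, because the documents give none. The SAP has no worked calcium value to reproduce.

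**1. Printed form and unit-consistent form.**

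- Printed: f = ¼ × [Ca − 0.8 × (0.1 × Alb − 4)] = Ca/4 − 0.02 × (Alb − 40)
- Unit-consistent, with calcium put on the scale of the 0.8 term before the division: g = ¼ × [4 × Ca − 0.8 × (0.1 × Alb − 4)] = Ca − 0.02 × (Alb − 40)

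The albumin slope is 0.02 mmol/L per g/L in both. Only the calcium term differs.

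**2. Worked values (mmol/L).**

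| Measured Ca | Albumin (g/L) | Printed f | Unit-consistent g |
|---|---|---|---|
| 2.4 | 40 | 0.60 | 2.40 |
| 2.2 | 30 | 0.75 | 2.40 |
| 3.4 | 40 | 0.85 | 3.40 |
| 3.4 | 45 | 0.75 | 3.30 |

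Rows two and four give the same printed result: ¼ × (2.2 + 0.8) = 0.75 and ¼ × (3.4 − 0.4) = 0.75. The unit-consistent values are 0.90 mmol/L apart, and the second is above the SAP's own high limit.

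**3. Rescaling the output does not help.** 4 × f = Ca − 0.08 × (Alb − 40). The albumin correction is then four times the intended 0.02 per g/L.

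**4. Range of the output.** f is lowest at low calcium with high albumin, and highest at the reverse.

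- Ca 2.0–3.4, Alb 25–45: f runs from ¼ × (2.0 − 0.4) = 0.40 to ¼ × (3.4 + 1.2) = 1.15; g runs from 1.90 to 3.70.
- Assumed normal ranges: f runs from ¼ × (2.1 − 0.8) = 0.325 to ¼ × (2.6 + 0.4) = 0.75; g runs from 1.90 to 2.70.

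Every printed result is below 2 mmol/L. The measured calcium needed for an output t is 4t + 0.8 × (0.1 × Alb − 4). At albumin 40 that is 8.0 mmol/L for t = 2 and 12.0 for t = 3. For t = 3 it is 10.8 at albumin 25 and 12.4 at albumin 45.

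**5. How many normal results would be graded severely low.** The CTCAE cut-offs are not in the documents, so the share is shown over a range. Let u = Ca − 2.1 (0 to 0.5) and v = 0.08 × (50 − Alb) (0 to 1.2). Then f = ¼ × (1.3 + u + v), and with values spread evenly the share below a cut-off c is the area where u + v < 4c − 1.3, divided by 0.5 × 1.2 = 0.6.

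| Cut-off c (mmol/L) | 4c − 1.3 | Area | Share |
|---|---|---|---|
| 0.40 | 0.3 | 0.045 | 8% |
| 0.50 | 0.7 | 0.225 | 38% |
| 0.60 | 1.1 | 0.425 | 71% |
| 0.70 | 1.5 | 0.580 | 97% |
| above 0.75 | above 1.7 | 0.600 | 100% |

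The even spread shows only how sensitive the share is to the cut-off. It is not a model of the trial population. The shares apply to both arms alike.

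**The case against.** The error is conceded; the case against is about its reach and cause.

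- **One analyte in a descriptive table.** Grades are tabulated parameter by parameter, and no test or stopping rule uses calcium grades. The by-visit summaries (6.3.1), the shift tables and Table 9 flags (6.3.2) and the listings (6.3: "Listings of individual laboratory measurements by subjects for all the parameters, both scheduled and unscheduled, will be provided") are not said to use the corrected value. Calcium abnormalities would stay visible there, and near-universal low calcium would be conspicuous to anyone reading the output. All of this stands and limits the damage, but none of those outputs is the Grade 3 and 4 endpoint.
- **The pooled count is uncertain.** No table counting participants with any Grade 3 or 4 laboratory abnormality is explicitly planned, and it is unclear whether the reference to unique participants in the endpoint extends to the laboratory item. This stands: inflation of such a count is conditional on its being produced, and its size depends on cut-offs that the documents do not give.
- **The cause is not settled.** If calcium inside the bracket were meant in mg/dL, the outer one quarter would act as the conversion to mmol/L and only the label would be wrong. A factor of 4 could also have been lost when the PDF was read. The sentence introducing the formula also gives calcium in mmol/L, which weighs against a simple label error. Either way, the replacement in mmol/L is the same, and the code has to be checked to learn which calculation was run.

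**Conclusion.** The concern holds. As printed, the formula returns exactly one quarter of the measured calcium at albumin 40 g/L, and it gives no result at or above 2 mmol/L anywhere in the range calcium 2.0–3.4 mmol/L, albumin 25–45 g/L. If programmed as written, the calcium CTCAE grades in both arms would be invalid, high calcium would not register, and any across-parameter Grade 3 and 4 count that includes calcium would be unreliable.

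The one-quarter result and the output range follow from the formula alone. The assumptions are that the derivation code follows the printed text and that the signed SAP prints the same formula. The exact grades, and so the number of false Grade 3 and 4 results, cannot be stated without the CTCAE cut-offs. Efficacy analyses and grades for other parameters are untouched. The error should be corrected because it sits in a primary safety output; nothing here suggests wider damage.

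**What to change.** Replace the formula in placebo-controlled SAP 6.3.2 with:

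corrected Ca (mmol/L) = Ca (mmol/L) − 0.02 × (Alb (g/L) − 40)

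This uses the SAP's own coefficients. Add the check that the result equals measured calcium at albumin 40 g/L. Compare the signed SAP and the derivation code with this form. If the code followed the printed version, rerun the calcium grade tables and any pooled Grade 3 and 4 laboratory count.

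The cost is one line of SAP text, one line of code and a rerun of the affected tables. No data collection or participant is affected.

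A separate housekeeping item in the same section has no bearing on CTCAE grading. Table 9 of both SAPs sets the high PCS limit for albumin at 625 g/L ("Albumin | ≤25 g/L | ≥625 g/L"), although albumin is part of total protein, whose own high limit is 100 g/L. That limit is a flag and not a ceiling, so this suggests a typing error without proving one. The value should be checked against its source.

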6.3.2 Qualitative analyses

For all qualitative analyses, all values will be included (not just the “analyzed record” within each visit window in the quantitative analyses).

Shift analyses

Laboratory data will be summarized using shift tables where appropriate for the active treatment (placebo-controlled and OLE) period. Each subject’s hematology, blood chemistry, coagulation and urinalysis (excluding microscopic examination) numeric values will be flagged as “low”,

“normal”, or “high” relative to the normal ranges of the central laboratory or as “unknown” if no result is available. Each subject’s urinalysis categorical values (parameters of protein, glucose, blood, and leukocyte esterase) will be flagged as “abnormal” if positive, “normal” if negative, or “unknown” if no value is available.

For each parameter, the analysis will be based on subjects with at least one post-baseline value. Shifts from baseline to high/low status will be presented for hematology, blood chemistry and urinalysis (specific gravity and pH) numeric parameters, and shifts from baseline to abnormal (positive) will be presented for urinalysis categorical parameters (protein, glucose, blood, and leukocyte esterase). Shift to low includes normal to low, high to low, and unknown to low; shift to high includes normal to high, low to high, and unknown to high. Subjects need to have at least one post-baseline evaluation and a baseline value either unknown or not low/high/abnormal (including missing) in order to be included in the analysis.

For early start subjects, the placebo-controlled baseline will be used and shifts that occurred in either placebo-controlled or OLE period will be included. For late start subjects, the active treatment period baseline will be used and shifts that occurred in the OLE period based on the active treatment period baseline will be included.

Potentially Clinically Significant laboratory abnormalities analyses

For hematology, blood chemistry and urinalysis, the number of subjects with potentially clinically significant (PCS) laboratory abnormalities post-baseline will be summarized for the parameters provided in Table 9 for the active treatment (placebo-controlled and OLE) period.

Subjects need to have at least one post-baseline evaluation in the active treatment period and a baseline value not potentially clinically significant (including missing) in order to be included in the analysis.

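### Table 9 of both SAPs sets the PCS High limit for albumin at 625 g/L, a value that cannot occur, so albumin can never be flagged as PCS high

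*SAP*

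**What the plan says.** Both SAPs plan a count of participants with potentially clinically significant (PCS) laboratory values after baseline, and both take the limits from a Table 9 in section 6.3.2 titled "Criteria to Determine Potentially Clinically Significant (PCS) Laboratory Abnormalities".

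In the placebo-controlled SAP the albumin row reads "Albumin | ≤25 g/L | ≥625 g/L" and the row below it reads "Total protein | ≤45 g/L | ≥100 g/L". Table 9 of the OLE SAP gives the same four limits for these two parameters.

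The table is operative in both places. The placebo-controlled SAP refers to Table 9 with the words "which also shows the thresholds used to determine PCS results" and adds a listing of participants with any PCS result after baseline. The OLE SAP says that "laboratory abnormalities post-baseline will be summarized for the parameters provided in Table 9 for the active treatment (placebo-controlled and OLE) period". Nothing elsewhere in either SAP corrects or explains the 625.

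A separate analysis in the same section does not use Table 9. In the shift tables of the placebo-controlled SAP, blood chemistry "values will be flagged as “low”, “normal”, or “high” relative to the normal ranges of the central laboratory". The OLE SAP has the same shift analysis.

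**The concern.** Albumin is one of the proteins that make up total protein, and Table 9 gives both in g/L. A sample cannot contain more albumin than total protein. A PCS High limit for albumin far above the PCS High limit for total protein is therefore a limit that no sample can reach.

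What is at stake is how one cell of a safety table reads. A zero count normally means that nobody crossed the limit. Here it would mean only that the limit could not be crossed, and the table would not let a reader tell the two apart. The zero could also stand beside a shift table that shows participants moving to high albumin.

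**Working it through.** The limit is tabulated, not derived, so there is no figure of the plan's to reproduce. The check is whether the value is consistent with the rest of the table and with the SAP's other use of albumin.

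**Inputs** (Table 9, section 6.3.2, the same in both SAPs)

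| Parameter | PCS Low | PCS High |
|---|---|---|
| Albumin | 25 g/L or below | 625 g/L or above |
| Total protein | 45 g/L or below | 100 g/L or above |

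**Step 1: albumin limit over total protein limit.**
- Low limits: 25 / 45 = 0.56. The part lies below the whole, as it should.
- High limits: 625 / 100 = 6.25. The order is reversed.

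**Step 2: can the criterion be met?** An albumin of 625 g/L requires a total protein of at least 625 g/L. That is 6.25 times the level at which the same table already calls total protein potentially clinically significant. In practice the criterion cannot be met.

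**Step 3: high limit over low limit, across the table.** Seventeen rows have both limits.
- Albumin: 625 / 25 = 25, the largest of the seventeen.
- Lymphocytes, the next largest: 12 / 0.8 = 15.
- Total protein: 100 / 45 = 2.2.

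This step is supporting evidence only, since a wide ratio is not in itself an error.

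**Step 4: the SAP's own reference point for albumin.** The corrected-calcium formula in section 6.3.2 of the placebo-controlled SAP contains the term 0.1 × albumin − 4. It is zero at albumin = 4 / 0.1 = 40 g/L, so the formula treats 40 g/L as the reference level. The tabulated limit is 625 / 40 = 15.6 times that.

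**Step 5: could the figure be a fault in the copy of the SAPs?** This is unlikely. The same value stands in both tables, and decimals in nearby rows are intact (10.7, 176.8, 9.7 and 1.7).

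**Step 6: which limits would be consistent?** The table bounds the answer only loosely: above its own albumin low limit of 25 g/L and below its total protein high limit of 100 g/L. A dropped decimal point would give 62.5 g/L, for which 62.5 / 100 = 0.625 and 62.5 / 25 = 2.5. That fits, but so do many other values.

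**The case against.** The best reply is that very little depends on this cell, and most of that reply stands.

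A reader might infer that high albumin cannot be detected anywhere in the planned outputs. The documents do not support that. Three planned outputs work without Table 9:
- the shift tables (section 6.3.2 of both SAPs), which class values against central laboratory ranges and use all values, not only the record selected for each visit window;
- the by-visit summaries (section 6.3.1 of both SAPs), which include the maximum;
- the individual laboratory listings (section 6.3 of the placebo-controlled SAP, to which the OLE SAP refers).

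Only the PCS High flag is disabled.

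A reader might also infer that the laboratory part of the primary safety endpoint is compromised. It is not. Grade 3 and 4 abnormalities are graded by CTCAE in the placebo-controlled SAP, without Table 9. The hepatotoxicity rules do not involve albumin.

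A third tempting inference is that the study report would declare the sample free of high albumin. The plan calls for a count and a listing. What the report would say in words cannot be known from it, and the same report would carry the shift counts and maxima.

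Finally, it is tempting to treat 62.5 g/L, or some sponsor standard, as the known correct value. Neither appears in the documents. Nor can we see the program, which may or may not carry the misprint. It can also be said that agreement between the two SAPs is weak confirmation, because one table may have been copied from the other. That is fair, but it explains how an error would spread and does not make the limit attainable.

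None of this repairs the cell. A criterion that cannot be met is wrong as written, even where other outputs cover part of the gap.

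**Conclusion.** The point holds, within narrow limits. In both SAPs the albumin PCS High limit of 625 g/L is 6.25 times the limit for total protein, of which albumin is a part. If the plan is followed as written, the PCS High albumin count is zero in every group and period whatever the data, and no participant is listed as PCS for that reason.

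The practical effect is small: one cell in a descriptive safety summary in each SAP. The documents do not allow the number of participants affected to be estimated; it is probably small. PCS Low albumin, all other PCS rows, CTCAE grading and efficacy are unaffected.

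The conclusion rests on two things: the tabulated values being what the SAPs contain, and albumin being a component of total protein in the same unit. It does not depend on any assumption about the intended value.

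**What to change.** The sponsor should confirm the albumin PCS High limit it intended. On the table's own figures it should lie above 25 g/L and below 100 g/L; a lost decimal point giving 62.5 g/L is only one possibility and should not be adopted without confirmation. Then correct the albumin cell in Table 9 of both SAPs, check that the threshold in the analysis program matches, and rerun the PCS summary and listing if they were produced with 625.

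The cost is one figure in each of two tables and a check of one program constant. This is a reporting threshold, so the correction changes no trial procedure and no other analysis.
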